##### **Inclusion Criteria:**

1. Report having been treated for an OOD within the past 6 months;
2. Age 18 years or older;
3. Scores “high risk” for heroin and/or non-medical use of prescription opioids on the NIDA modified ASSIST (i.e.,  $\geq 27$ );
4. Be able to understand the study, and having understood, provide written informed consent in English;
5. Access to a phone (for TTIP-PRO intervention and phone follow-up);
6. Be willing to have their intervention audio recorded and rated if randomized to TTIP-PRO;
7. Have an opioid-positive baseline/screening urine drug screen.

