##### **Exclusion Criteria:**

1. In the judgment of the investigator, would not be expected to complete the study protocol (e.g., due to relocation from the clinic area, probable incarceration, etc.)
2. Current engagement in addiction treatment;
3. Residence more than 40 miles from the location of follow-up visits;
4. Inability to provide sufficient contact information (must provide at least 2 reliable locators);
5. Prior participation in the current study.

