## 1.4 Study assessments

### 1.4.1 Participant Measures

**Primary outcome measure.** Entered MAT (Yes/No) – The determination of whether the participant enrolled in a MAT program within the 12-month follow-up will be based on participant self-report, confirmed by clinic records, obtained with the proper release of information (ROI) from the participant.

**Secondary outcome measures.** Opioid overdose (Yes/No)–Determination of whether the participant experiences an OOD within 12-month follow-up will be based on participant self-report.

Opioid use will be assessed with the Timeline Follow-back (TLFB) procedure and urine drug screens (UDS). At each assessment point, the TLFB will be used to assess self-reported substance use for the 28 days prior to the visit. The rapid UDS will include screens for substances of abuse. Urine samples will be collected using temperature monitoring and the validity of urine samples will be checked with the use of a commercially available adulterant test.

**Process measures.** Barriers to Treatment Inventory (BTI) - This 25-item Likert-scale questionnaire has seven internally consistent subscales relating to Absence of Problem, Negative Social Support, Fear of Treatment, Privacy Concerns, Time Conflict, Poor Treatment Availability, and Admission Difficulty. The Fear of Treatment subscale will be evaluated as a mediator of TTIP-PRO's efficacy (see **Fig. 1**).

Thoughts about abstinence (TAA) - Participants' commitment to abstinence from illicit substances will be assessed with the TAA. This measure assesses the participant's desire to quit, expected success in quitting and estimated difficulty in avoiding relapse. Both desire to quit and expected success in quitting will be evaluated as mediators (see **Fig. 1**).

The Opioid Overdose and Treatment Awareness Survey (OOTAS). The OOTAS assesses knowledge about OOD and MAT and is comprised of four sections: 1) OOD risk factors; 2) signs of an OOD; 3) how to respond to an OOD; and 4) myths about MAT. The total OOTAS score will be evaluated as a mediator of TTIP-PRO's efficacy (see **Fig. 1**).

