### 5.2 Data Analysis

All analyses will be completed on the ITT sample using SAS (SAS Institute, Inc.). Statistical tests will be conducted at a 5% Type I error rate (two-sided) for all measures. It has been recommended that effect sizes be provided rather than using the Bonferroni procedure to adjust for multiple-comparisons; thus, effect sizes and 95% confidence intervals (CI's) will be computed for each treatment effect. For each efficacy analysis, demographic/baseline characteristics and length of time since last OOD will be selected for inclusion in the model using the corrected Akaike Information Criterion (AICC) as the optimizing criterion. For missing data, multiple imputation methods will be used and the resulting model compared to the non-imputed model. **Participant Analyses**-The primary hypothesis, that a significantly greater proportion of TTIP-PRO, relative to control, participants will enter MAT within 12-month follow-up will be tested using a logistic regression (a generalized linear model with a logistic link). Secondary analyses. The key secondary hypothesis, that a significantly lower proportion of TTIP-PRO, relative to control, participants will have a recurring OOD within 12-month follow-up will be tested using a logistic regression (a generalized linear model with a logistic link). The secondary hypothesis that TTIP-PRO, relative to control, participants will have a significantly greater reduction in illicit opioid use will be tested using two outcomes, one based on self-report and the other on UDS results. The proportion of self-reported use days will be treated as a binomial variable and regressed using logistic mixed model regression (random-intercept generalized mixed-model regression with a logistic link function). UDS results (positive for illicit opioids vs. not positive), will be treated as a binary variable which will also be regressed using logistic mixed-model regression. For both outcomes, the effects of interest will be treatment and treatment-by-time interaction.

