Power: A pilot study necessitates a limited sample size, and is more useful for showing feasibility than providing an effect size estimate. The proportion of patients who will enroll in a MAT program is unknown for both the TTIP-PRO and control group. Thus, we based the estimated proportions on a recent randomized trial comparing buprenorphine administration during medical hospitalization and linkage to office-based buprenorphine post-discharge to buprenorphine detoxification. In that study, the linkage patients were more likely to enter office-based buprenorphine treatment (72.2%) compared to the detox group (11.9%). The linkage condition was much more intensive than TTIP-PRO and, thus, it is expected that the TTIP-PRO enrollment rate will be considerably less than that observed for the linkage group. Assuming that 12% of our control group enrolls in MAT, and a total sample size of 80, we would have 80% power using a two-tailed test and  $\alpha = .05$  to detect a TTIP-PRO effect for a MAT enrollment rate of  $\geq 39\%$ . In our SBIRT trial, our 12-month follow-up rate was 78%. If 78% of participants complete the 12-month follow-up ( $n=62$ ) in the proposed trial, we would have 80% power (assuming 12% engagement for the control group, a two-tailed test, and  $\alpha = .05$ ) to detect a TTIP-PRO effect for a MAT enrollment rate of  $\geq 46\%$ .

**Peer Interventionist Analyses** - The hypotheses related to the Peer Interventionists will be tested with descriptive statistics. The proportion of Peer Interventionists: 1) attending the training who complete training and certification within the expected 4-hour timeframe and 2) who report being satisfied or very satisfied with their experience as a Peer Interventionist will be calculated.

**Analyses for Exploratory Aims-** E1 – Testing the validity of the HOPI and PORS. The HOPI was designed to include two subscales (i.e., personally relevant; credible). Factor analyses will be used to determine if the HOPI does, in fact, yield two factors corresponding to the intended subscales. Since the HOPI uses Likert-scale variables, the factor analysis will be based on polychoric correlation. A logistic generalized linear model regression will be used to test the PORS score as a predictor of 1 year OOD rates. The strength of predictive validity will be expressed both as the estimated odds ratio and by area under a ROC curve.

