2. Primary and secondary outcome measures: Enrollment in MAT (Yes/No) within the 12-month follow-up period is the primary outcome measure. Secondary outcomes include experiencing an OOD (Yes/No) within the 12-month follow-up and change in opioid use, as measured by the Timeline Follow-back (TLFB) procedure and urine drug screens (UDS), between baseline and 12-month follow-up. Process measures include: Barriers to Treatment Inventory- the Fear of Treatment subscale will be evaluated as a mediator of TTIP-PRO’s efficacy. Thoughts about abstinence will assess desire to quit illicit opioid use and expected success in quitting, which will be evaluated as mediators. The Opioid Overdose and Treatment Awareness Survey (OOTAS) assesses knowledge about OOD and MAT; the total OOTAS score will be evaluated as a mediator of TTIP-PRO’s efficacy. The Helpfulness of Peer Intervention (HOPI) will assess the degree to which participants perceived TTIP-PRO to be personally relevant and credible; the total score will be tested as a moderator. Peer Interventionist Measures include: 1) the Peer Volunteer Experience Questionnaire (PVEQ) will be used to obtain feedback from peer volunteers delivering TTIP-PRO; and 2) the PROMIS 10-item measure for Global Health.
3. Inclusion/exclusion criteria:

This project includes two types of participants: 1) the participants who may receive the TTIP-PRO intervention, referred to as participants, and 2) the participants who will serve as Peer Interventionists.

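### The treatment-by-time test for self-reported use days makes no allowance for a person's use shifting between visits, so its 5% error rate and 95% CI need not hold

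*Combined protocol and SAP*

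**What the plan says.** Section 1.4.1 sets the data: at each assessment "the TLFB will be used to assess self-reported substance use for the 28 days prior to the visit". Each visit therefore gives a count of use days out of 28. Table 1 schedules this at baseline and at 3, 6 and 12 months.

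Section 5.2 names the model: "The proportion of self-reported use days will be treated as a binomial variable and regressed using logistic mixed model regression (random-intercept generalized mixed-model regression". The link is logistic. It continues: "For both outcomes, the effects of interest will be treatment and treatment-by-time interaction". Earlier in the same section: "Statistical tests will be conducted at a 5% Type I error rate (two-sided) for all measures", with a 95% CI for each treatment effect. Appendix B, III.3 repeats all of this. Appendix B, I.2 defines the outcome as "change in opioid use, as measured by the Timeline Follow-back (TLFB) procedure and urine drug screens (UDS), between baseline and 12-month follow-up".

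Neither analysis section mentions a random slope, a participant-by-visit effect, a dispersion term or robust standard errors. Covariate selection by AICC and multiple imputation are planned, but neither addresses variation within a person between visits.

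**The concern.** The participant intercept cancels out of a person's change over time. Once it has cancelled, the model's only yardstick for treatment-by-time is binomial sampling of 28 days. Any real movement in a person's use beyond that is not counted, and the interaction standard error is too small.

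The plan gives its own reasons to expect movement. Entrants must "Have an opioid-positive baseline/screening urine drug screen" and are excluded for "Current engagement in addiction treatment". Some are expected to start treatment ("Assuming that 12% of our control group enrolls in MAT"). Exploratory aim E2 treats MAT engagement as a mediator of the level of opioid use.

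The outcome is defined as change, and treatment-by-time is the effect that tests change. A chance difference could be reported as significant, with too narrow an interval. Section 5.2 relies on effect sizes and CIs in place of a multiplicity adjustment, and Section G says promising results would support a larger trial. The stakes are still limited: this is one of two effects on one of two measures of a non-key secondary outcome, and no decision rule depends on it.

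**Working it through.** **Inputs from the documents.** 28 days per window (1.4.1); visits at 0, 3, 6 and 12 months (Table 1); 80 randomised 1:1, so 40 per arm (1.1); 12-month follow-up 78%, so 22% missing, applied at each follow-up visit (5.2, power); 12% of controls entering MAT (5.2, power).

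**Assumed, because the documents give no figure.** Participant SD 1.5 on the logit scale; mean logit 0 (14 of 28 days) unless stated; the size of any shift, shown as a range.

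**1. Mechanism by hand.** Planned model: Y_ij ~ Bin(28, p_ij), logit p_ij = x_ij'β + b_i. Suppose the truth adds a visit-level shift with SD σ_v. The sampling variance of one visit's observed logit is about 1/(28p(1−p)); at p = 0.5 this is 1/7 = 0.143. The true variance is 0.143 + σ_v², so the standard error should be larger by √((0.143 + σ_v²)/0.143):
- σ_v = 0.25: √(0.205/0.143) = 1.20
- σ_v = 0.5: √(0.393/0.143) = 1.66
- σ_v = 1.0: √(1.143/0.143) = 2.83

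For people using on nearly all or nearly no days, p(1−p) is smaller and binomial noise larger, so the average ratio over participants is lower.

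**2. The plan's 5% with no shifts.** The planned model was fitted by maximum likelihood to simulated null trials, with Wald tests. Rejection was 6% with categorical time (3 df) and 4% with linear time (400 trials). A second simulation used visit mean logits 1.5/0.7/0.5/0.5, monotone dropout to 78% and likelihood ratio tests (500 trials); it gave 3.6% and 5.6%. The stated level holds when nobody's use shifts.

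**3. Shifts from MAT entry, null true.** Each person in both arms has a 12% chance of entering MAT at a random time, after which log-odds of use fall by the amount shown (2,000 trials each; Monte Carlo SE 0.5 points at 5%, 1.0 at 25%). SE, SD and coverage are for the 12-month contrast.

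| Fall | Days of 28, average user | Rejects, 3 df | Rejects, linear | Model SE | True SD | 95% CI coverage |
|---|---|---|---|---|---|---|
| 1 | 14 to 7.5 | 7% | 8% | 0.157 | 0.172 | 92% |
| 2 | 14 to 3.3 | 16% | 15% | 0.157 | 0.215 | 85% |
| 3 | 14 to 1.3 | 25% | 23% | 0.157 | 0.249 | 78% |

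Coverage agrees with 2Φ(1.96 × SE/SD) − 1. At fall 2, 1.96 × 0.157/0.215 = 1.43, which gives 85%.

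With near-daily use at entry (mean logit 2.5, about 26 of 28 days), falls of 2 and 3 give 20% and 36% (3 df), and 21% and 29% (linear). With dropout rising to 22% at 12 months instead, fall 2 gives 16.5% and 16.7%, so the missingness pattern is not decisive.

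**4. Independent visit-to-visit noise, null true.** Logit SD 0.25 / 0.5 / 1.0 gives 15% / 32% / 71% (3 df) and 9% / 19% / 40% (linear). The second simulation gave 11.6% / 32.8% / 70.8% and 7.4% / 19.0% / 37.6%. A random slope of SD 1 logit per year gave 20.4% and 27.6%.

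**5. Scope.** The visit-averaged treatment effect rejected in 4.5–6.0% of trials in every null setting of steps 3 and 4. The UDS model has one binary result per visit and is not materially affected.

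**6. Remedy.** Participant-clustered sandwich variance multiplied by N/(N−k), with reference F(q, N−k); N = 80, k = 9 (categorical) or 5 (linear), q = 3 or 1. Null rejection was 3.6–6.1% in ten settings under both codings. Without the correction it was 6.7–9.6% (3 df) and 4.7–7.5% (linear). A participant-by-visit random effect gave 5.2% / 4.2% / 5.2% at falls 1 / 2 / 3 with categorical time, but 8.5% / 7.3% / 8.5% with linear time, and 12.7% with linear time, near-daily use and fall 3. These runs used 316 to 716 trials each.

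**The case against.** *The plan omits a detail rather than making an error: it never says the standard errors are model-based, and the remedy keeps the model.* In part. But the outcome distribution and the random-effects structure are both named. Fitted as named, that likelihood fixes the variance, and nothing in the text tells the analyst to do otherwise.

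*The size is unanchored.* This stands. No document gives the between-person SD, the visit-to-visit variation or the effect of MAT on use days. At fall 1 the inflation is small. Part of the inflation is chance imbalance in who enters MAT: with exactly 5 entrants per arm, falls 2 and 3 give 13% and 19% (3 df), and 9% and 12% (linear). The corrected test is then conservative, at 1–3%.

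*The full planned procedure was not simulated.* True: AICC selection and multiple imputation were left out. Confidence is high for the direction and conditional for the size.

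*This is a pilot, which Section 5.2 itself values more for feasibility than for effect estimation.* That limits the importance. It does not make a stated 5% level or 95% interval correct.

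*The remedy is imperfect and costs power.* One repeat of 500 trials with near-daily use and fall 3 gave 7.8% for the corrected 3 df test (Monte Carlo SE about 1.2 points). A 1,000-trial repeat kept it within 4.3–6.1% in every setting run, that one included, so 7.8% is consistent with simulation noise. The loss of power is real in part; no size-adjusted comparison was made.

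**Conclusion.** The concern holds. As written, the use-days model understates the standard error of treatment-by-time whenever a person's use shifts between visits beyond binomial sampling, and the plan's own conceptual model implies that it will. The direction does not depend on the assumed values. The size does: in the MAT-entry scenario, actual error runs from near nominal (7–8% at a fall of 1) to about a quarter of null trials (23–25% at a fall of 3), and higher with near-daily use at entry. The visit-averaged treatment effect, the UDS model, the primary analysis and the overdose analysis are not materially affected. It should be fixed because the change is small, but it does not threaten the trial's main conclusions.

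**What to change.** In Section 5.2 and Appendix B, III.3, keep the random-intercept binomial model and add one sentence. It should say that the treatment-by-time test and its CI for use days use participant-clustered empirical (sandwich) standard errors, multiplied by N/(N−k) on the variance scale, with an F(q, N−k) or matching t reference. It should also say whether time is categorical or linear. The correction must be named, because the uncorrected version over-rejects. A participant-by-visit random effect is an acceptable alternative only with categorical time. Random-slope and beta-binomial models were not tested as remedies and are not proposed.

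**Cost.** One sentence in each place and one SAS option; no extra data. The CI for the 12-month contrast becomes about 1.2 / 1.5 / 1.7 times as wide at falls 1 / 2 / 3, and 1.2 / 1.6 / 2.4 times at visit SD 0.25 / 0.5 / 1.0. Power falls. If 12% of controls and 39% of TTIP-PRO participants enter MAT (the difference Section 5.2 is powered for) and log-odds fall by 2, rejection goes from 71% to 29% (3 df) or from 77% to 47% (linear), in 600 trials per setting. Part of the higher figures is the inflated error rate.

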## 2.2 TTIP-PRO

An overview of TTIP-PRO, as evaluated in this pilot trial, is provided in **Fig. 2**. A full description of the development and initial testing of TTIP-PRO is described in [name] et al. TTIP-PRO consists of two parts: 1) an information packet which includes three reports (“Personal Overdose Risk Factors Report”; “Medication Assisted Treatment (MAT) Report”; and the “Opioid Overdose Information Report”) generated from the participant’s responses to two surveys and information about how to access treatment at a UC ASD (UC Health/UCPC) MAT program; 2) a 20-minute telephone intervention delivered by Peer Interventionists.

**Information Collected to Tailor the Intervention.** *The Personal Opioid-Overdose Risk Survey (PORS).* The PORS assesses an individual’s OOD risk factors. It only includes risk factors for which there is documented evidence and scoring for each item was based on the strength of the evidence that the factor increases risk. In order to tailor the questions to reference only the type(s) of opioids used by a given individual, there are three versions of the PORS, one for heroin-only users, one for prescription opioid-only users and one for those who use both heroin and prescription opioids. *The Opioid Overdose and Treatment Awareness Survey (OOTAS).* The OOTAS assesses knowledge about OOD and MAT; like the PORS, there are three versions of the OOTAS to reflect the type(s) of opioids used. The OOTAS is comprised of four sections: 1) OOD risk factors; 2) signs of an OOD; 3) how to respond to an OOD; and 4) myths about MAT. The first 3 sections include only evidence-based items supported by a recent literature review, while items for the 4th section are based on both a literature review and on input from the medical staff of the UC-affiliated methadone program.

**The TTIP-PRO Computer Program.** The TTIP-PRO data entry and report-generation system has been programmed into REDCap, a software toolset and workflow methodology for collection and management of clinical research data. After an operator enters all relevant information for a particular patient (type of opioid used, responses to the PORS and OOTAS questions), the TTIP-PRO system automatically generates three

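### For self-reported use days the plan names two effects but no deciding contrast, leaves baseline adjustment to AICC, and disagrees with Appendix B on the target; some ordinary readings lose much of the power

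*Combined protocol and SAP*

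**What the plan says.** Section 5.2 hypothesises that illicit opioid use falls more with TTIP-PRO than with control, and tests this on self-report and on urine screens. For self-report, "The proportion of self-reported use days will be treated as a binomial variable and regressed using logistic mixed model regression", with a random intercept. It then adds: "For both outcomes, the effects of interest will be treatment and treatment-by-time interaction". Appendix B section III.3 repeats this.

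On covariates, section 5.2 says that "demographic/baseline characteristics and length of time since last OOD will be selected for inclusion in the model using the corrected Akaike Information Criterion". Baseline use is not named as a required term.

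Section 1.4.1 sets the recall window: "the TLFB will be used to assess self-reported substance use for the 28 days prior to the visit". Table 1 schedules the TLFB at baseline and at months 3, 6 and 12.

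Appendix B section I.2 defines the secondary outcome as "change in opioid use, as measured by the Timeline Follow-back (TLFB) procedure and urine drug screens (UDS), between baseline and 12-month follow-up".

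**The concern.** A hypothesis about reduction needs one contrast that measures reduction. The plan gives two terms and leaves open the coding of time, the role of the baseline record, the visit to which the treatment term refers, and which term decides. These choices change what is tested:

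- With baseline rows in the model and baseline as reference, the treatment term is the gap between arms before treatment.
- Averaged over all four visits, the treatment term is diluted by a visit that precedes treatment.
- With linear time, the interaction looks for arms that keep diverging to month 12. The peer contact is "a 20-minute telephone intervention delivered by Peer Interventionists", given at about two weeks (Table 1), so a sustained or fading effect is plausible too.

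Section 5.2 makes no multiplicity adjustment. An open choice of term and coding therefore lets the conclusion be settled after the data are seen. The point concerns use days in particular: baseline use days vary between people, whereas everyone enters with an opioid-positive urine screen.

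**Working it through.** The documents state no power, variance or effect size for use days, so there is no planned figure to reproduce. The section 5.2 power statement concerns MAT entry only.

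**Inputs.** From the documents: visits at 0, 3, 6 and 12 months, 1:1 allocation, two-sided 5%. Assumed: normal approximation, total variance 1 per visit, equal correlation r = 0.3, 0.5 or 0.7 between visits, no dropout. Arm differences are counted positive when they favour TTIP-PRO.

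**Formulas.** With n per arm, λ = (n/2) × contrast² ÷ per-arm variance, and power ≈ Φ(√λ − 1.96). Centred times are −5.25, −2.25, 0.75, 6.75, with sum of squares 78.75. For a sustained effect d at months 3, 6 and 12:

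- A, follow-up average adjusted for baseline: contrast d, variance (1+2r)/3 − r²
- B, the same average unadjusted: contrast d, variance (1+2r)/3
- C, main effect over four visits: contrast 0.75d, variance (1+3r)/4
- D, linear slope: contrast 5.25d/78.75, variance (1−r)/78.75, so λ is proportional to 0.35d²/(1−r)
- E, 3-df categorical interaction: λ proportional to 0.75d²/(1−r), where 0.75 = 3 − 9/4

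The effect d is scaled so that A has λ = 7.85, which is 80% power.

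| r | A variance | B: λ, power | C: λ, power | D: λ, power | E: λ, power |
|---|---|---|---|---|---|
| 0.3 | 0.443 | 6.52, 72% | 4.12, 53% | 1.74, 26% | 3.73, 34% |
| 0.5 | 0.417 | 4.91, 60% | 2.94, 40% | 2.29, 33% | 4.91, 43% |
| 0.7 | 0.310 | 3.04, 41% | 1.77, 26% | 2.84, 39% | 6.08, 52% |

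**Other shapes, same d.**

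- d, 0.75d, 0.5d: the average is 0.75d, so λ = 7.85 × 0.5625 = 4.41 and A has 56%. The slope over 12 months is 12 × 1.6875d/78.75 = +0.26d, the right sign, with power 7–8%.
- d, d/2, 0: the average is 0.5d, so λ = 1.96 and A has 29%. The slope is 12 × (−1.875d)/78.75 = −0.29d, the wrong sign. E has 31–49% and beats A.
- d/4, d/2, d (steady growth in months): slope 6.5625d/78.75, average 0.583d. Efficiency of D relative to A is [0.547/(1−r)] ÷ [0.340/variance of A], which is 1.02 at r = 0.3 and 1.66 at r = 0.7.

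**A month-12 contrast instead.** Adjusted for baseline, its variance is 1 − r². For the sustained effect, λ = 7.85 × 0.443/0.91 = 3.82 (50%) at r = 0.3 and 7.85 × 0.310/0.51 = 4.77 (59%) at r = 0.7.

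**Check in the plan's own model family.** A simulation used a binomial on 28 days with a random-intercept logistic model, 40 per arm, 300 trials per scenario. Assumed: control logits 1.3, 0.5, 0.3, 0.2; intercept SD 1.3; average follow-up log odds ratio −0.5; no extra visit-to-visit variation.

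- Constant effect: adjusted average 0.96, linear interaction 0.79. The treatment term in that linear model had 0.12.
- Categorical time with baseline as reference: the treatment term rejected in about 6% of trials, so it carried no information. The average of the three interaction terms had 0.98.
- Effect fully gone by month 12, linear time: the interaction was significant in favour of control in 69% of trials. The treatment term still favoured TTIP-PRO, with power 0.45.

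With an added visit-to-visit SD of 0.8, the interaction tests rejected a true null in 34% (linear) and 62% (3-df) of trials, so their powers cannot be compared in that setting.

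**The case against.** A reader might infer that the plan tests a time slope, and so will miss a real reduction or report it with the wrong sign. The documents do not support that. Neither section 5.2 nor Appendix B section III.3 says that time is linear. With categorical time the interaction terms are the arm differences in change from baseline, so it is also too strong to say that neither named effect measures reduction. A reversed interaction needs both linear time and an effect that wanes strongly; partial fading to 0.5d keeps the right sign.

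Other objections also stand in part:

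- Effect shape is unknown. Section 5.2 treats MAT engagement as a mediator of opioid use, and MAT entry accrues over 12 months, so a growing effect is possible. The average contrast then has no advantage over the slope.
- The normal model overstates the slope's loss in at least one setting. The simulated 0.79 against 0.96 implies relative efficiency of about (2.77/3.71)² = 0.56, not the 0.22–0.36 implied by the D column (λ divided by 7.85).
- AICC may select baseline use, so adjustment is uncertain rather than absent.
- Appendix B already names a 12-month target. Choosing the average instead is the sponsor's decision.
- This is a secondary outcome, not the key one, in a pilot that plans effect sizes with 95% confidence intervals.

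None of this supplies the missing contrast or reconciles section 5.2 with Appendix B section I.2.

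**Conclusion.** The concern holds as one of an undefined target and an unforced baseline covariate. For a sustained effect, the ordinary readings of the named terms have 26–53% power where a baseline-adjusted follow-up average has 80%. Leaving baseline out of that average alone lowers it to 41–72%. These figures rest on the normal, compound-symmetry approximation with assumed r of 0.3 to 0.7 and on the sustained shape. No single contrast is best for every shape: the slope matches or beats the average for growth steady in months (102–166% efficiency), and the 3-df test beats it for d, d/2, 0 (31–49% against 29%). The case for change is that one contrast should be fixed in advance and that baseline use, already collected, should always be used. It should be settled before analysis, but it does not threaten the trial's primary result.

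**What to change.** In section 5.2 and Appendix B section III.3, model use days at months 3, 6 and 12 with arm, categorical visit, arm-by-visit and the participant's baseline 28-day use proportion. Make that last term a forced covariate, exempt from AICC selection.

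Name one deciding 1-df contrast: the arm difference averaged over months 3, 6 and 12, or the month-12 difference if Appendix B section I.2 states the real intention. Report the visit-specific differences with 95% confidence intervals as description, and reword Appendix B section I.2 to agree.

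While the model text is open, say how visit-to-visit variation beyond the binomial will be handled.

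The cost is wording only, since every measurement is already scheduled. The average contrast is less sensitive to a late or growing effect. The month-12 contrast has less power for a sustained one (50–59% under the same assumptions).
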